## 8.4 Demographic and Baseline Characteristics

Demographic and baseline clinical characteristics for the study participants will be summarized by study arm using the general analysis rules describe above. Variables of interest include mother demographics, gender, gestational age, race and ethnicity, and in-hospital clinical outcomes at the time of birth.

#### 9 EFFICACY ANALYSES

## 9.1 Overview of Efficacy Analysis Methods

- All efficacy analyses will be performed on the ITT population.
- All efficacy variables will be summarized by treatment group. Count (N), mean, standard deviation, minimum, and maximum will summarize continuous efficacy variables (e.g., postmenstrual age); median, 1st quartile, 3rd quartile, minimum, and maximum will be calculated for count efficacy variables (e.g., number of days of hospitalization); whereas number and percent will summarize categorical efficacy variables (e.g., death).
- Analyses of the primary outcome are separately discussed in Section 9.3. Analyses of other
  dichotomous outcomes will be performed using robust Poisson regression models, with both log
  and linear link functions, to estimate adjusted relative risks and risk differences. Efficacy models
  will be adjusted for stratification by clinical site and gestational age. Unless otherwise noted, all
  analyses of continuous efficacy variables will be performed using median or robust Poisson
  regression.

Models will be adjusted for clinical site and gestational age. If there are not enough patients per clinical site to include the variables in the models as fixed effects, clinical site will be included as a random intercept to account for correlation between outcomes of patients treated by the same clinical site or similar sites will be combined.

## 9.2 Efficacy Variables

Primary and secondary efficacy variables are described in the table below.

| Variable                               | Type  | Definition   |  |
|--|-------|--|--|
| Primary Outcome                        |       |  |  |
| Number of days of hospitalization      | Count | The number of days between randomization and hospital discharge. This outcome is censored at 48 weeks PMA and at time of transfer or death   |  |
| Secondary Outcomes                     |       |  |  |
| Number of days to physiologic maturity | Count | Physiologic maturity is defined:  i. Temperature: out of the incubator for at least 48 hours with normal body temperature  ii. Feeding: oral feeding at a volume of at least 140 ml/kg for 48 hours or growing on less than 140 ml/kg/day for at least 48 hours  iii. Respiratory: apnea-free for at least 5 consecutive days  This outcome is censored at 48 weeks PMA. |  |

| Variable  | Type       | Definition  |
|---|------------|---|
| Number of days to physiologic maturity - Temperature                        | Count      | Physiologic maturity is defined:  i. Temperature: out of the incubator for at least 48 hours with normal body temperature  This outcome is censored at 48 weeks PMA.  |
| Number of days to
physiologic maturity –
Feeding                      | Count      | Physiologic maturity is defined:  i. Feeding: oral feeding at a volume of at least 140 ml/kg for 48 hours or growing on less than 140 ml/kg/day for at least 48 hours  This outcome is censored at 48 weeks PMA.            |
| Number of days to
physiologic maturity -
Respiratory                  | Count      | Physiologic maturity is defined:  i. Respiratory: apnea-free for at least 5 consecutive days This outcome is censored at 48 weeks PMA.  |
| Post-menstrual age at discharge   | Continuous | The post-menstrual age of the infant at discharge censored at 48 weeks PMA and at time of transfer or death   |
| Number of all-cause
readmissions within first 4
weeks post-discharge  | Count      | Number of hospital readmissions including apneic events and apparent life-threatening events during first 4 weeks following hospital discharge. The outcome is censored at 48 weeks PMA.                                    |
| Number of all-cause
readmissions within second 4
weeks post-discharge | Count      | Number of hospital readmissions including apneic events and apparent life-threatening events during second 4 weeks following hospital discharge. The outcome is censored at 48 weeks PMA.                                   |
| Number of all-cause
readmissions within first 8
weeks post-discharge  | Count      | Number of hospital readmissions including apneic events and apparent life-threatening events during first 8 weeks following hospital discharge. The outcome is censored at 48 weeks PMA.                                    |
| Number of all-cause sick visits within first 4 weeks post-discharge         | Count      | Number of all cause sick visits, urgent care, emergency room, or other non-scheduled/routine health care provider office visits during first 4 weeks following hospital discharge. The outcome is censored at 48 weeks PMA. |
| Number of all-cause sick visits within second 4 weeks post-discharge        | Count      | Number of all cause sick visits, urgent care, emergency room, or other non-scheduled/routine health care provider office visits during last 4   |

| Variable  | Type        | Definition  |
|---|-------------|---|
|   |             | weeks following hospital discharge. The outcome is censored at 48 weeks PMA.  |
| Number of all-cause sick visits within first 8 weeks post-discharge | Count       | Number of all cause sick visits, urgent care, emergency room, or other non-scheduled/routine health care provider office visits during first 8 weeks following hospital discharge. The outcome is censored at 48 weeks PMA. |
| All-cause Mortality   | Categorical | Demise of Infant  |

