The protocol will allow for individual study site centers to use their own discharge criteria, but for the purposes of the definition of secondary outcome of the trial, infants must have reached physiologic maturity, which includes a) out of an incubator for at least 48 hours, b) oral feeding at volume of at least 140 ml/kg/day or growing on less than 140 ml/kg/day for at least 48 hours, and be apnea-free for at least 5 consecutive days. Infants who are still in the hospital at 44 weeks PMA will have the study medication (caffeine/placebo) discontinued. Analysis will be done by intention to treat. If an infant is discharged before meeting the definition of physiologic maturity, it will be noted for analysis at the conclusion of the trial. The weight within 48 hours of discharge will be used for the caffeine/placebo home administration. The dose will not be adjusted for weight gain after discharge. The practice of discharging infants home on open-label caffeine will not be a part of the trial. However, should it occur, it will be noted as a protocol deviation and will be noted for subsequent analysis.

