## 3.1.2 Secondary Aims

1. To evaluate the effect of continuing treatment with caffeine citrate in the hospital on number of days to reach physiologic maturity from randomization to discharge up to 48 wks PMA.

- 2. To evaluate the effect of treatment with caffeine until 28 days after hospital discharge on all-cause readmissions to a hospital (including apneic and/or apparent life-threatening events) within the first 8 weeks after discharge by 48 wks PMA.
- 3. To evaluate the effect of treatment with caffeine until 28 days after hospital discharge on the number of all-cause sick visits to urgent care, emergency rooms, or health care provider's office (including apneic and/or apparent life-threatening events) within the first 8 weeks after discharge by 48 wks PMA.
- 4. To evaluate the side effects and adverse events of caffeine continuation in the hospital and after discharge up to 4 weeks post study drug administration.
- 5. To assess the hypothetical cost-savings by the reduction in number of days of hospitalization as a financial benefit of the trial's interventions.

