## 3.2.2 Secondary Outcomes

- 1. The number of days to physiologic maturity after randomization up to 48 wks PMA. Physiologic maturity will be defined as follows:
  - a) Temperature: out of the incubator for at least 48 hours with normal body temperature
  - b) Feeding: oral feeding at a volume of at least 140 ml/kg/day or growing on less than 140 ml/kg/day for at least 48 hours
  - c) Respiratory: apnea-free for at least 5 consecutive days
- 2. Post menstrual age at discharge up to 48 wks PMA, censoring at time of transfer or death (status).
- 3. The number of all cause readmissions, including apneic events and apparent life-threatening events (ALTE), to the hospital within the first four weeks, second four weeks, and first eight weeks combined after discharge from the hospital by 48 wks PMA.
- 4. The number of all cause sick visits to urgent care, emergency room or health care provider office within the first four weeks, second four weeks, and first eight weeks combined after discharge from the hospital by 48 wks PMA.
- 5. Safety outcome measures pre-hospital discharge:
  - a) Weight gain from randomization until status (discharge up to 48 wks PMA, with censoring at time of transfer or death). The weight gain may also be assessed using percentiles including birthweight percentiles.
  - b) The number of days after randomization until status that infant had at least two consecutive heart rates >200 documented at least 3 hours apart (when infant not crying).
  - c) Treatment for high blood pressure initiated after randomization until status.
  - d) The number of episodes between randomization and status that infant was placed NPO for ≥ 24 hours.
  - e) The use of anti-reflux medications started between randomization and status
  - f) The number of days that significant apnea/bradycardia, as defined by documentation of infant receiving any of the following between randomization and status: open label caffeine, other methylxanthines, doxapram, continuous positive airway pressure (CPAP) or ventilatory support for apnea/bradycardia.
  - g) The presence of documented and treated arrhythmias between randomization and status, not due to tachycardia or bradycardia.

h) The onset of documented seizures, as defined by treating with anti-convulsants, between randomization and status.

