The protocol will allow for individual study site centers to use their own discharge criteria, but for the purposes of the definition of secondary outcome of the trial, infants must have reached physiologic maturity, which includes a) out of an incubator for at least 48 hours, b) oral feeding at volume of at least 140 ml/kg/day or growing on less than 140 ml/kg/day for at least 48 hours and be apnea-free for at least 5 consecutive days. Infants who are still in the hospital at 44 weeks PMA will have the study medication (caffeine/placebo) discontinued. Analysis will be done by intention to treat. If an infant is

discharged before meeting the definition of physiologic maturity, it will be noted for analysis at the conclusion of the trial. The weight within 48 hours of discharge will be used for the caffeine/placebo home administration. The dose will not be adjusted for weight gain after discharge. The practice of discharging infants to home on open-label caffeine will not be a part of the trial. However, should it occur, it will be noted as a protocol deviation and will be noted for subsequent analysis.

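### Days to physiologic maturity has no pre-specified end of observation for infants who are discharged, transferred or die before meeting the definition, and the planned regression does not handle censoring

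*SAP*

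**What the plan says.** The efficacy table in SAP 9.2 has four rows for physiologic maturity: the composite, and temperature, feeding and respiratory maturity separately. Each carries the same rule: "This outcome is censored at 48 weeks PMA". The outcome list in SAP 3.2.2 agrees: "The number of days to physiologic maturity after randomization up to 48 wks PMA".

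Two other rows of that table go further. For the primary outcome: "This outcome is censored at 48 weeks PMA and at time of transfer or death". For PMA at discharge: "The post-menstrual age of the infant at discharge censored at 48 weeks PMA and at time of transfer or death".

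The secondary aim sets a different window for maturity: "number of days to reach physiologic maturity from randomization to discharge up to 48 wks PMA" (SAP 3.1.2; the Protocol's secondary hypotheses and secondary specific aims say the same).

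Discharge before maturity is foreseen. SAP 4.8 states: "The protocol will allow for individual study site centers to use their own discharge criteria". Protocol 5.2.3 then says: "If an infant is discharged before meeting the definition of physiologic maturity, it will be noted for analysis at the conclusion of the trial". SAP 4.8 repeats this.

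The planned models for this outcome are median or Poisson regression (Protocol 6.2; SAP 9.1, 9.3 and 9.4).

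**The concern.** Maturity requires, among other things, five consecutive apnea-free days. Discharge follows local criteria and a local apnea countdown, so an infant can go home before the definition is met. In-hospital observation stops there, and home monitor recordings are not used (SAP 4.8). Transfer or death before maturity raises the same question. For all of these infants, SAP 9.2 names only a limit that lies weeks after observation has ended, and noting the event is neither a value nor a censoring rule.

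This is the first-listed secondary outcome. Protocol 4.5.1 also expects the trial to show whether other aspects of maturity delay discharge. Caffeine is meant to change apnea and the timing of discharge, so the share leaving unmet may differ by arm. Without a rule, the coding would be chosen when the data are analysed, and part of any difference between arms could come from that choice.

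**Working it through.** The plan states no figure on this point, so there is none to reproduce.

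**1. Rules side by side**

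| Place | 48 weeks PMA | Discharge | Transfer or death |
|---|---|---|---|
| SAP 9.2, primary outcome | yes | is the event | yes |
| SAP 9.2, PMA at discharge | yes | is the event | yes |
| SAP 9.2, maturity and three components | yes | not stated | not stated |
| SAP 3.2.2, maturity | yes | not stated | not stated |
| SAP 3.1.2, aim for maturity | yes | ends the window | not stated |

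The aim and the definition differ on discharge. Neither covers transfer or death.

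**2. How far away the limit is.** Randomization is at 33 0/7 to 35 6/7 weeks PMA. 48 weeks is 48 × 7 = 336 days. From 33 0/7 (231 days) that is 105 days; from 35 6/7 (251 days) it is 85 days. The planning figures for stay are 12 and 14 days.

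**3. Effect on the median of one arm.** Assumptions not in the documents: a share q leaves unmet, at random with respect to true time to maturity, and time to maturity has a median of 14 days (borrowed from the planning figure for stay) with either normal SD 10 or lognormal sigma 0.77.

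If leavers are coded at the 48-week limit, the observed median falls at percentile 0.5/(1 − q) of the true distribution. With z the normal quantile of that percentile, the shift is 10z (normal) or 14(exp(0.77z) − 1) (lognormal).

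- q = 5%: percentile 0.526, z = 0.066. Shift 0.66 or 0.73, about 0.7 days.
- q = 10%: percentile 0.556, z = 0.140. Shift 1.40 or 1.59 days.

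If random leavers are excluded, the shift is about 0.

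**4. Upper bound.** Suppose instead that every leaver is among the fastest to mature. Excluding them moves the median to percentile q + (1 − q)/2; coding them at the limit moves it to 0.5 + q.

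| q | Excluded | Coded at limit |
|---|---|---|
| 5% | 0.63 to 0.69 days | 1.26 to 1.42 days |
| 10% | 1.26 to 1.42 days | 2.5 to 3.0 days |

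**5. Effect on the mean (Poisson model).** Here the assumed distribution is lognormal, median 14, log-SD 0.6, so the true mean is 14 × exp(0.6²/2) = 16.8 days. The limit averages 95 days (midpoint of 85 and 105), and leavers exit at 60% to 100% of their true time (average 80%).

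- 5% coded at the limit: 0.95 × 16.8 + 0.05 × 95 = 20.7 days.
- 5% coded at the day of leaving, as if observed: 0.95 × 16.8 + 0.05 × 0.8 × 16.8 = 16.6 days.

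The medians under the same assumptions, by simulation, are 14.6 and 13.8 days.

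**6. Two arms, no true effect, 10% versus 5% random leavers** (same simulation). Coding at the limit gives a false difference of 0.7 days in the median and 4.0 days in the mean. Coding at the day of leaving gives about −0.2 days in both. Exclusion gives about 0, but only because leaving was simulated as random.

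**The case against.** The strongest reply is that the aim already ends the window at discharge, so only the wording of SAP 9.2 needs tidying. SAP section 5 also keeps infants who do not complete the study in every analysis for which they have data, and SAP 9.4 lets other models be considered for the secondary outcomes. Part of this stands: the intended window can be inferred. But the aim gives no rule for an infant who reaches its end unmet and is silent on transfer and death. SAP 9.4 names survival models only as an example for the primary outcome.

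A second reply is that few infants will be affected. Protocol 4.5.1 says most neonatologists observe for at least five days after stopping caffeine, the feeding criterion has an alternative, and planned transfer to a non-network site is an exclusion. This is reasonable, but the documents give no rate.

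Three stronger readings are tempting, and the documents do not support them.

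- A reader might infer that infants who leave early have no usable value at all. A component met before leaving remains valid; the gap concerns the composite and any unmet component.
- A reader might infer that the plan must either drop these infants or carry them to 48 weeks. It says neither, and the aim permits a third reading, ending observation on the day of leaving.
- A reader might take the upper bound in step 4 as the expected bias. It requires one arm only and all leavers among the fastest to mature. An infant sent home unmet matures after discharge and need not be a fast maturer.

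**Conclusion.** The concern holds as a gap in specification. SAP 9.2 and the aim disagree on where observation ends, no rule covers infants who leave unmet, and ordinary median or Poisson regression does not accommodate censoring.

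Its size depends on an unknown share of leavers and on how they are coded. With random leavers in one arm, coding at the 48-week limit shifts that arm's median by about 0.7 days at 5% and 1.4 to 1.6 days at 10%. Exclusion shifts it by about 0. A mean model or leavers who are mainly early maturers would give larger shifts; equal shares of random leavers in both arms would give roughly no false difference. The 14-day median and the spreads are assumptions.

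The outcome is secondary and its p-values are descriptive (SAP 7.7). The primary result is unaffected. The change is worth making, but the trial's main conclusion does not depend on it.

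**What to change.** In SAP 9.2, for the composite and each component:

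1. End observation at the earliest of maturity, discharge, transfer, death or 48 weeks PMA, and align SAP 3.2.2 and 3.1.2 with this.
2. Use a method that handles censoring (a time-to-event model or censored median regression), adjusted for center and gestational-age group, with death as a competing event.
3. Report by arm the share discharged, transferred or dead before maturity.
4. Add one sensitivity analysis for informative early discharge, for example varying the assumed time from leaving to maturity. This is needed because treating discharge as ordinary censoring assumes that leaving is unrelated to time to maturity, so step 2 alone would not remove bias from early discharge that differs by arm.

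The cost is SAP wording and slightly more analysis work on a secondary outcome. SAP 4.8 already collects the dates of status, last apnea, last tube feed and last incubator day.

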## 9.3 Primary Analysis Methods

For the primary analysis, the number of days of hospitalization between randomization and discharge will be compared between the caffeine citrate and placebo groups using either median or robust Poisson regression models. The model will include a fixed effect for treatment group. The model will also be adjusted for the design effect of stratification by site and gestational age. Estimates, p-values and 95% confidence intervals will be presented for treatment group comparisons. In an intent-to-treat fashion, all data will be included in the primary model based on their randomized treatment, regardless of the treatment administered to the patient. If there are important baseline characteristics that differ between randomized treatment groups by chance, additional sensitivity analyses may be conducted to evaluate the impact of those imbalances.

We will examine treatment heterogeneity for the primary outcome by adding interaction terms between treatment and study center, as well as treatment and gestational age group, and following NIH guidelines, treatment and sex. If any of these interaction terms are close to statistical significance (p<0.1), for treatment heterogeneity by study center, we will attempt to identify centers where the treatment effect may be different (although the statistical power available to conduct such analyses will be fairly limited). If there is indication of treatment heterogeneity by GA group and/or sex, we will conduct stratified analyses by GA group and/or sex to quantify the treatment effect separately by GA group/sex.

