### 6.2. STATISTICAL ANALYSIS PLAN

The primary analysis will compare number of days of hospitalization from randomization to discharge, death, transfer or 48 weeks PMA, whichever occurs first between the intervention and control groups using median regression controlling for study center and GA group (the two stratification factors for this trial). Likewise, the treatment effect for the secondary outcomes (number of days to physiologic maturity after randomization, number of readmissions and number of sick visits) will be compared using either median regression or a Poisson regression model controlling for study center and GA group.

Secondary analyses will evaluate whether other models better fit the distributions for these outcomes (for example, survival analysis models for the primary outcome and negative binomial or log linear models for the secondary outcomes).

We will examine treatment heterogeneity for the primary outcome by adding interaction terms between treatment and study center, as well as treatment and GA group. If any of these interaction terms are close to statistical significance ( $p<0.1$ ), for treatment heterogeneity by study center, we will attempt to identify centers where the treatment effect may be different (although the statistical power available to conduct such analyses will be fairly limited). If there is

indication of treatment heterogeneity by GA group, we will conduct stratified analyses by GA group to quantify the treatment effect separately by GA group.

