#### Interim Efficacy Monitoring

Statistical interim efficacy monitoring will be conducted by the Data Coordinating Center after 25%, 50% and 75% of the babies enrolled into the trial complete eight-week follow up period. At each of these interim looks, the primary outcome will be compared by (blinded) treatment group as per the analysis plan in section 6.2. O'Brien Fleming stopping bounds for efficacy will be used to preserve an overall Type-I error rate of 0.05 for the primary outcome. Thus, stopping bounds for efficacy will be established if  $p < 5 \times 10^{-5}$  at 25%,  $p < 0.004$  at 50% and  $p < 0.018$  at 75% of interim data accrual. In the event that these stopping bounds are reached, the Data Safety and Monitoring Committee may recommend termination of the trial for efficacy. In addition to the primary outcome, secondary efficacy outcomes collected in this trial (see section 4.2) will also be examined by treatment group.

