## 4.5 Masking and Data Lock

## 4.6 General Masking Procedures

This is a double-blind, placebo-controlled clinical trial. As such, neither site staff nor the parent/guardians that administer the study drug to the patient will be aware of the treatment assignment. Only the research pharmacists at the clinical sites and designated personnel at the DCC (Study Manager, Data Manager and Study Statistician) will be unblinded. All clinical caregivers and investigators, including the DCC PI will remain masked to the study drug assignment. Any intentional or unintentional unmasking will be reported as a protocol deviation in the data management system.

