#### **6 SAMPLE SIZE DETERMINATION**

To obtain a two-day difference in the primary outcome of days from randomization to discharge, from 14 days to 12 days, with a power set at 90%, a significance of 0.05, and a 5% attrition, the trial would require 587 infants per group (intervention and placebo) for a total of 1174 infants, assuming a two-tailed, non-parametric test comparing median LOS in the two groups. With a power set at 80%, under the same assumptions and significance, the trial would require 439 infants per group for a total of 878 infants. The minimum required sample size for this trial will be 878 (439 in each treatment group), but enrollment will continue until either the available supply of study drug is exhausted or expires in approximately August 2023 (accounting for full in-hospital and post-discharge follow-up), whichever comes first.

There are approximately 3000 infants born between 290/7 and 33 6/7 weeks gestation per year in the NRN. A review of 100 infants in the NICU at one of the largest centers in the NRN showed that 37% of infants within this cohort were treated with a methylxanthine. This is similar to NRN data showing that approximately 1000 (one-third) of infants receive caffeine therapy. The following table shows scenarios for approximate time to completion of the trial as a function of consent rate and NICHD center involvement:

| Consent Rate (%) | Time to Completion (mo), all sites | Time to Completion (mo), half sites |
|------------------|------------------------------------|-------------------------------------|
| 50               | 24                                 | 48                                  |
| 60               | 20                                 | 40                                  |
| 70               | 18                                 | 36                                  |
| 80               | 15                                 | 30                                  |

| Effect Size (days) | Significance | Power (%) | Attrition (%) | Sample Size |
|--------------------|--------------|-----------|---------------|-------------|
| 14 to 10           | 0.05         | 80        | 5             | 226         |
| 14 to 10           | 0.05         | 90        | 5             | 302         |
| 14 to 12           | 0.05         | 80        | 5             | 878         |
| 14 to 12           | 0.05         | 90        | 5             | 1174        |

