## **Interim Efficacy Monitoring**

Statistical interim efficacy monitoring will be conducted by the DCC after 25%, 50% and 75% of the babies enrolled into the trial complete eight-week follow up period. At each of these interim looks, the primary outcome will be compared by (blinded) treatment group using the methods outlined in Section 9. O'Brien Fleming stopping bounds for efficacy will be used to preserve an overall Type-I error rate of 0.05 for the primary outcome. Thus, stopping bounds for efficacy will be established if p  $< 5 \times 10^{-5}$  at 25%, p < 0.004 at 50% and p < 0.018 at 75% of interim data accrual. In the event that these stopping bounds are reached, the DSMC may recommend termination of the trial for efficacy. In addition to the primary outcome, secondary efficacy outcomes collected in this trial will also be examined by treatment group.

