## 7.5 Masked Data Review

A masked data review of the primary outcome and secondary outcomes for this study will be performed by the protocol team. This review will occur prior to completion of the primary analyses prior to any official unblinding. This will include a presentation of descriptive statistics (e.g., means, standard deviations, percentiles for continuous variables and counts and percentages of categorical variables) of the selected outcomes and model predictor variables.

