#### 13 CHANGES TO THE ANALYSES PLANNED IN THE PROTOCOL

None at this time. Additional analyses motivated by observations in the final outcome data may be conducted, but these will be clearly identified as post-hoc analyses in any publication and will not be specifically addressed via updates to the SAP.

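### The protocol fixes median regression as the primary test; the SAP allows median or robust Poisson regression, gives no rule or date for choosing, and declares no change

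*SAP*

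**What the plan says.** Protocol 6.2 compares the primary outcome "between the intervention and control groups using median regression controlling for study center and GA group". Its median-or-Poisson alternative appears only in the next sentence, which covers secondary outcomes: days to physiologic maturity, readmissions and sick visits.

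SAP 9.3 carries the alternative over to the primary outcome, which "will be compared between the caffeine citrate and placebo groups using either median or robust Poisson regression models". SAP 9.1 refers the reader to 9.3 for the primary outcome. SAP 9.4 treats the search for better-fitting models as a secondary analysis. Neither supplies a rule for choosing. SAP 13 reports changes from the protocol's analyses as "None at this time".

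The interim efficacy looks split the same way. The protocol says "the primary outcome will be compared by (blinded) treatment group as per the analysis plan in section 6.2", which is median regression. SAP 7.4 says "the primary outcome will be compared by (blinded) treatment group using the methods outlined in Section 9", which is the open choice.

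SAP 6 bases the sample size on one type of comparison: "assuming a two-tailed, non-parametric test comparing median LOS in the two groups".

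On masking, SAP 4.7 withholds assignments until database lock. SAP 7.5 plans a masked review of outcome distributions: "This review will occur prior to completion of the primary analyses prior to any official unblinding". SAP 4.6 keeps investigators masked, but "designated personnel at the DCC (Study Manager, Data Manager and Study Statistician) will be unblinded".

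**The concern.** SAP 7.7 sets one confirmatory test at two-sided 0.05. That rate holds only if the test is settled without sight of results by arm. Here two models are allowed and no blind choice is documented, so a reader of the final report could not tell whether the reported model was picked before or after those results were known.

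The models also answer different questions. Median regression gives a difference in median days. Robust Poisson gives a ratio of mean days, or a difference of means under a linear link, and 9.3 does not state the link. With skewed stays the two can lead to different conclusions from the same data. The interim stopping levels (5×10⁻⁵, 0.004, 0.018) are therefore not attached to one defined statistic.

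**Working it through.** **1. The plan's own figure.** The sample size is 878 for 14 versus 12 days at 80% power, and 1174 at 90%, with two-sided 0.05 and 5% attrition. No SD is given, so I solved for it from n per arm = 2(z₀.₉₇₅ + z_power)² SD²/δ², then divided by 0.95. With SD 10.3 and δ = 2:
- 80% power: 2 × (1.960 + 0.842)² × 10.3²/4 ≈ 416.5, so 417. Then 417/0.95 = 438.9, so 439 per arm and 878 in total.
- 90% power, same formula: 1176, against 1174 stated.
- The 14-to-10 rows give 222 and 296, against 226 and 302.

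The table is consistent with one SD of about 10.3 days (about 9.6 to 10.1 if a rank-test efficiency of 0.864 or 0.955 is built in). It supports a comparison of typical stay; nothing in it covers a choice between two models. Analysable infants at the minimum size: 439 × 0.95 ≈ 417 per arm, used below.

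**2. The two statistics.** With treatment as the only covariate:
- Median regression: z₁ = (difference in medians)/√(s₁²/4n + s₂²/4n), where s is the estimated sparsity (inverse density at the median).
- Robust Poisson, log link: z₂ = ln(mean₁/mean₂)/√(v₁/(n·mean₁²) + v₂/(n·mean₂²)), where v is the sample variance.

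The worst case counts a trial as positive if either p-value is below 0.05. For two tests of exact size 0.05, the result would be 5% if they were identical and 1 − 0.95² = 9.75% if independent.

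**3. Null simulation without covariates.** 20,000 replicates per row, assumed stays with median 14 and SD about 6 to 18:

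| Assumed stays | Median alone | Poisson alone | Either |
|---|---|---|---|
| Lognormal, log-SD 0.4 | .045 | .047 | .075 |
| Lognormal, log-SD 0.574 | .044 | .052 | .080 |
| Lognormal, log-SD 0.8 | .044 | .050 | .082 |
| Gamma, shape 2 | .044 | .050 | .076 |
| Gamma, shape 4 | .046 | .052 | .079 |
| Weibull, shape 1.2 | .045 | .048 | .077 |
| Weibull, shape 1.5 | .046 | .051 | .078 |

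The correlation of the two statistics was 0.60–0.77. False results favouring caffeine came to 3.6–4.1%, against a nominal 2.5%. A separate set (6,000 replicates; lognormal SD 9.6, gamma SD 9.9, heavy-tailed lognormal SD 16.4) gave 8.0–8.3% for either.

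**4. With covariates.** The documents give no number of centers; 15 plus GA group was assumed.

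| Adjusted run | Median alone | Either |
|---|---|---|
| 6,857 replicates | .060 | .093 |
| 2,400 replicates, continuous stays | .060 | .094 |
| 2,400 replicates, whole-day stays | .045 | .083 |
| 1,200 replicates, continuous stays | not recorded | .083 |
| 1,200 replicates, whole-day stays | not recorded | .078 |

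In the first row, Poisson alone was .051 and false results favouring caffeine were 4.5%. The open choice adds 9.3 − 6.0 = 3.3 points there and 8.3 − 4.5 = 3.8 points in the third row. The Monte Carlo standard error of the 1,200-replicate figures is about 0.8 points.

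**5. Four looks.** This uses the stated interim levels and an assumed final level of 0.043, since the plan states none. Median alone 4.3–4.6%, Poisson alone 4.9–5.6%, either 7.8–8.4%.

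**6. How often the choice decides the result.** The same 6,000-replicate set, 417 per arm, single final look:

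| Scenario | Power, median | Power, Poisson | Models disagree at 0.05 |
|---|---|---|---|
| 2-day shift, lognormal | .84 | .84 | 16% |
| 2-day shift, gamma | .70 | .83 | 20% |
| 2-day shift, heavy tail | .52 | .42 | 29% |
| Stays scaled by 12/14, lognormal | .89 | .96 | 10% |
| Stays scaled by 12/14, gamma | .75 | .95 | 21% |
| Stays scaled by 12/14, heavy tail | .57 | .70 | 28% |

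Under the null the models disagree in 6–7% of trials. Neither model is always the more powerful.

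**The case against.** SAP 9.3 goes on to describe a single model, so it offers a choice of one rather than two tests with the better result reported. The worst-case rates describe conduct the SAP does not plan. That stands: they bound what the wording leaves open and do not predict what will happen. The case for correction rests on the text.

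The 9.3% is also not all due to the choice, because median regression alone reached 6.0% in that run. That stands too, and about 8% is the steadier figure.

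The SAP keeps the protocol's method and lists it first, sizes on medians, and summarises days of hospitalization by median and quartiles. So it loosens the protocol's target without replacing it. But a mean contrast remains equally permitted as the primary result.

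Limited unblinding at the coordinating center is normal where interim reports are prepared there, and no text says the unblinded statistician chooses the model. The masked review would be a natural decision point. The text does not give it that role, though, and interim reports already show the primary outcome by group A and B while the model is open.

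The SAP is dated December 2022 and drug supply was expected to expire about August 2023. Some interim looks may have passed; the documents do not say.

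**Conclusion.** The concern holds. Protocol and SAP contradict each other on the trial's only confirmatory test, at the interim and final looks, and SAP 13 is wrong to report no change. Nothing in the text ensures or records a model choice made blind to results.

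If the model is fixed blind, each test alone ran at 4.4–6.0% in single-look simulations, and the harm is confined to an unclear estimand. If the better of the two were reported, two-sided type I error would be about 8% (7.5–8.3% unadjusted, 7.8–9.4% adjusted), with 3.6–4.5% instead of 2.5% falsely favouring caffeine. These rates depend on assumed stay distributions, 417 infants per arm and, when adjusted, 15 centers. The contradiction does not depend on any of them.

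**What to change.** In SAP 9.3, name median regression adjusted for center and gestational-age group as the sole primary analysis. State in SAP 7.4 that the same model serves the interim efficacy looks. List robust Poisson and survival models as sensitivity analyses. This follows the protocol and matches the sample-size basis.

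If the sponsor prefers robust Poisson, the SAP should state the link, declare the change in SAP 13, and have the choice made and dated by people who have seen no results by group. The masked review in SAP 7.5 could do this on pooled data, if the SAP says so.

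The median choice has costs the sponsor should weigh first. The headline would rest on the median even if the effect lies mainly in long stays. Power at 417 per arm can fall below Poisson's (0.70 versus 0.83 for a 2-day shift with gamma stays), though the order reverses with heavy tails. Adjusted median regression alone ran at 6.0% in two of the simulations with continuous stays, so the SAP should also state how its standard error is obtained.

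The change is SAP wording only, with no extra data or patients. It carries full weight only if made before unblinding.
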